1.1 Power Analysis

We performed a sample size analysis to determine the appropriate number of subjects to enroll in order to assure that we would achieve adequate statistical power. For an alpha level of .05, and an anticipated effect of 0.5 (medium), and a power of .8, we need a total of 102 (50 in each rehabilitation group) for a one-tailed (Strategic Advantage > Informational Advantage) directional hypothesis. Based on these analyses we plan to enroll 100 participants. These individuals will be randomized into the two intervention arms.

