1.2 Statistics for Primary Outcome Measures

Virtual Multiple Errands Test (VMET): We will evaluate intervention efficacy by comparing the performance of the VR-EFT group to that of the VR-BHT group on performance-based measures of executive function ability related to daily life. This first test will evaluate near-transfer of intervention skills to the VMET, a test of executive functions evaluated in a computerized format. VMET requires working memory, planning, coordinating, and prioritizing, thus it serves as a global, performance-based measure of executive function. We will evaluate change on total number of errors from the pre-intervention baseline using a 2 (group) x 2 (testing session) repeated-measures ANOVA followed by Bonferroni-correct post-hoc tests to evaluate the significance of simple mean comparisons. We predict a significant time-by-group interaction in which the VR-EFT group will perform more accurately relative to the VR-BHT group at the post-intervention test, but not at the pre-intervention test. In the event that this measure proves insensitive, we will compute and analyze sub-scores based on strategy errors, completion errors, and rule-violation errors applying an additional Bonferroni multiple comparison correction for the use of three sub-measures.

TBI Awareness Questionnaire: We will evaluate far-transfer to overall Awareness score, which is a reflection of actions carried out in a real life setting. Performance (averaged over sub-domains) will be evaluated using a 2 (group) x 2 (testing session) repeated-measures ANOVA, followed by post-hoc tests corrected for multiple comparisons. We predict a time-by-group interaction with superior life outcomes reported by the Strategic Advantage group over the Informational Advantage group at the post-intervention time point only with no reliable differences expected at the pre-intervention phase.

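### Section 1.1 sizes the trial for a one-tailed test, but section 1.2 tests both primaries with a non-directional interaction F; like for like, power is about 0.70, not 0.80

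*SAP*

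**What the plan says.** Section 1.1 (Power Analysis) sets the design inputs: "For an alpha level of .05, and an anticipated effect of 0.5 (medium), and a power of .8". It sizes the trial "for a one-tailed (Strategic Advantage > Informational Advantage) directional hypothesis" and concludes "we need a total of 102 (50 in each rehabilitation group"), then "Based on these analyses we plan to enroll 100 participants".

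Section 1.2 (Statistics for Primary Outcome Measures) analyses change in total errors on the Virtual Multiple Errands Test (VMET) "using a 2 (group) x 2 (testing session) repeated-measures ANOVA followed by Bonferroni-correct post-hoc tests". It plans the same form of ANOVA for the TBI Awareness Questionnaire. It states a direction for each outcome. For VMET: "We predict a significant time-by-group interaction in which the VR-EFT group will perform more accurately relative to the VR-BHT group". For the questionnaire: "We predict a time-by-group interaction with superior life outcomes reported by the Strategic Advantage group over the Informational Advantage group".

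Section 1.2 gives no significance level, no signed contrast, no rule for halving the p-value, and no statement that the interaction is to be read one-sided.

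**The concern.** The power calculation and the primary analysis describe different decision rules. A one-tailed test rejects only when the difference favours the Strategic Advantage arm. The ANOVA interaction F rejects for a large difference in either direction, and at .05 it sets a higher bar in the favourable direction.

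Two things are at stake. First, the 80% power claim may not describe the test that will be run. Second, some results are positive under one section and negative under the other. If the choice between them is left until the data are in, the false-positive risk in the favourable direction can rise from 2.5% to 5% for each primary outcome.

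**Working it through.** **Inputs**
- From section 1.1: alpha .05, effect 0.5, target power .8, one-tailed, 102 needed, 100 to be enrolled, taken as 50 per arm.
- From section 1.2: 2x2 repeated-measures ANOVA, with the time-by-group interaction as the predicted finding.
- Assumed: equal arms, no dropout, and 0.5 as a standardized difference in change (varied in step 5).

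**Step 1. Reproduce the plan's figure.** For a two-sample t-test with n per arm, the noncentrality is d·√(n/2) on 2n − 2 degrees of freedom.
- One-tailed .05, d = 0.5, power 0.80: n = 50.15, so 51 per arm and 102 in total. Power at 51 per arm is 0.806.
- Two-sided .05, same inputs: n = 63.77, so 64 per arm and 128 in total (power 0.795 at 63 per arm, 0.801 at 64).

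The 102 is therefore a one-tailed two-sample t-test. The two-sided calculation does not give it.

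**Step 2. Identify the section 1.2 test.** With two groups and two sessions, the interaction F has 1 and N − 2 degrees of freedom and equals t², where t is the two-sample t on change scores. At N = 100, F exceeds its .05 critical value exactly when |t| > 1.984, which is the two-sided t-test at .05.

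**Step 3. Power at the planned size.** With 50 per arm and d = 0.5, the noncentrality is 0.5 × √25 = 2.5 on 98 degrees of freedom.

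| Test | Critical t | Power |
|---|---|---|
| One-tailed .05 | 1.661 | 0.799 |
| Two-sided .05 (the ANOVA F) | 1.984 | 0.697 |
| One-sided .025 | 1.984 | 0.697 |

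Two-sided power reaches 0.80 at d = 0.566.

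**Step 4. Results on which the two sections disagree.** The critical observed difference is the critical t times √(2/50) = 0.2.
- One-tailed: 1.661 × 0.2 = 0.332.
- Two-sided: 1.984 × 0.2 = 0.397.

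The probability of falling between them is 0.05 − 0.025 = 0.025 under no effect, and 0.799 − 0.697 = 0.102 at d = 0.5.

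**Step 5. Dependence on the effect scale.** If 0.5 is in raw-score SD units, with no baseline difference and pre-post correlation r, the change-score effect is 0.5/√(2(1 − r)). The SAP gives no r, so these values are assumed:

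| r | Change-score d | One-tailed power | Two-sided power |
|---|---|---|---|
| 0.3 | 0.423 | 0.675 | 0.553 |
| 0.5 | 0.500 | 0.799 | 0.697 |
| 0.7 | 0.645 | 0.941 | 0.892 |

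On this reading, two-sided power reaches 0.80 at r of about 0.61.

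**The case against.** The best defence reads the two sections as one document. Section 1.1 gives the only level and the only sidedness in the SAP, section 1.2 predicts the same direction for both primaries, and nowhere does the SAP say two-sided. A 1-df interaction can be read with a sign, so the sponsor may simply have meant one-tailed .05 throughout, and then power is essentially as stated (0.799). Section 1.2 also plans a between-group comparison at post-test, which resembles the comparison that section 1.1 sizes.

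Part of this stands. One-tailed testing may well have been intended, and the fix leaves that open. But a predicted direction is a hypothesis and not a rejection rule: an F test rejects in both directions unless the plan says otherwise. The post-test comparisons follow the interaction and carry a Bonferroni correction, so they are not the test sized in section 1.1 either.

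It is also fair to say that 0.70 is conditional. Step 5 shows two-sided power from 0.55 to 0.89 under other assumptions. It should be read as a like-for-like comparison, not as a forecast of the trial's power. The unstated effect scale and correlation matter here only as limits on that figure.

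**Conclusion.** The concern holds. The sample size is correct for a one-tailed t-test, but section 1.2 names a test that is two-sided as written. Holding everything else fixed, the difference costs about 10 percentage points of power at the planned 50 per arm. At any given effect scale and correlation, the one-tailed figure is the higher of the two. The two-sided test keeps 80% power only if 0.5 is a raw-score effect and the pre-post correlation is about 0.61 or more, and the SAP states neither.

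This should be settled before the data are seen, because it fixes the rule by which each primary outcome is judged. The figures assume equal arms and no dropout. They do not include multiplicity across the two primaries or the mismatch between 102 and 50 per group, which are separate points.

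**What to change.** Keep 100 participants. The sponsor should say which sidedness was meant and state one sidedness and one level in both sections, by one of two routes.

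- **A. Two-sided.** Restate section 1.1 along these lines: *With 50 per arm, the two-sided .05 test of the group-by-time interaction has about 70% power for a standardized difference in change of 0.5, and 80% for 0.57.* Give the effect scale and any assumed pre-post correlation.
- **B. One-sided.** Add to section 1.2: *The interaction is tested one-sided at level [x] as a signed t-test on change scores, favouring VR-EFT (fewer VMET errors; better Awareness score).* At d = 0.5, power is 0.80 for a level of .05 and 0.70 for .025.

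Either route costs only SAP wording in sections 1.1 and 1.2 and no added participants. Under A the stated power becomes less favourable.

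A separate option, not needed to resolve the mismatch, is a baseline-adjusted ANCOVA. With 0.5 in raw-score SD units, the effect becomes 0.5/√(1 − r²) on 97 degrees of freedom. Two-sided power is then 0.74, 0.77, 0.82 and 0.93 for assumed r of 0.3, 0.4, 0.5 and 0.7, and reaches 0.80 from r of about 0.47. This uses data already planned, but it changes the primary analysis and would need an amendment before the data are seen. Sidedness would still have to be stated.

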1.3.1 Performance on Neuropsychological Tests

The neuropsychological tests will be evaluated according to the procedures outlined for the use of the ANAM and the relevant scoring procedures for each additional test in the planned battery. These scores will be organized by primary domain and analyzed using 2 (group) x 2 (testing session) ANOVAs. The domains of interest for the neuropsychological battery are as follows: working memory, goal maintenance, verbal fluency and general cognition. These same groupings will be applied to the ANAM data as well with the exception of verbal fluency, as this domain is not examined in our ANAM battery.

Analysis of Game Performance Data Acquired During Intervention

Data from the Strategic Advantage and Informational Advantage weekly modules will be analyzed by total number of task errors and by completion times for each task in order to determine the degree of individual improvement on tasks from Day 1 to Day 5 during each of the four weeks. For the long term memory module we will also analyze total recall scores across the week. We will apply this same analysis to the overall recall scores obtained in Week 4 during the composite game-based simulation.

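### Section 1.1 enrols 100 against a stated need of 102 (50 per group) with no margin for loss before the post-intervention test, so the power of .8 describes evaluable participants, not those enrolled

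*SAP*

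**What the plan says.** Section 1.1 of the SAP sets out the calculation: "For an alpha level of .05, and an anticipated effect of 0.5 (medium), and a power of .8", "for a one-tailed (Strategic Advantage > Informational Advantage) directional hypothesis". Its result is "we need a total of 102 (50 in each rehabilitation group"). The next step is enrolment: "Based on these analyses we plan to enroll 100 participants. These individuals will be randomized into the two intervention arms". Section 1.1 makes no adjustment between the calculated need and the recruitment figure.

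Section 1.2 defines the analysis that the calculation is meant to serve. For the VMET: "We will evaluate change on total number of errors from the pre-intervention baseline using a 2 (group) x 2 (testing session) repeated-measures ANOVA". The Awareness score is analysed with the same two-by-two design, and for both outcomes the predicted result is a time-by-group interaction.

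Section 1.3.1 shows what lies between the two sessions. The game data are to describe "the degree of individual improvement on tasks from Day 1 to Day 5 during each of the four weeks".

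**The concern.** A power calculation returns the number of participants who must supply the data that enter the test. Section 1.1 uses that number as the number to recruit. In a two-session repeated-measures ANOVA as normally run, a participant without a post-intervention session drops out of the interaction test, and section 1.2 describes no method for using incomplete pairs. Four weeks of sessions give some opportunity for loss.

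The figures in section 1.1 also disagree slightly with each other: 2 × 50 = 100, not 102, and enrolment follows the smaller figure. Enrolment therefore carries no margin on one figure and is two short on the other. Correcting that mismatch would not deal with loss, because enrolling 102 would also leave no margin.

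What is at stake is how the result is read. If some participants are lost, a null finding on the VMET or the Awareness score could be taken as coming from a trial with power .8 for an effect of 0.5 when its power was somewhat lower.

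**Working it through.** **Inputs.** From section 1.1: one-tailed alpha .05, power .8, effect 0.5, two groups, 50 per group (so 1:1). Two assumptions are mine. First, 0.5 is a standardized mean difference (d) in the contrast that is tested; section 1.1 does not name the metric. Second, loss is equal in the two arms at 0, 5, 10 or 20%; the SAP gives no rate.

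**Reproducing the plan's figure.** For n per arm, the t-test has 2n − 2 degrees of freedom and noncentrality d × √(n/2). Power is the probability that a noncentral t with those parameters exceeds the one-sided 5% critical value.

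- n = 51: noncentrality 0.5 × √25.5 = 2.525, critical value 1.660 on 100 df, power .806.
- n = 50: noncentrality 0.5 × √25 = 2.500, critical value 1.661 on 98 df, power .799.

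The smallest n per arm that reaches .8 is 51, which gives the stated total of 102. The normal approximation gives 2 × ((1.645 + 0.842)/0.5)² = 49.5, rounded up to 50 per arm, or 100. So 102 and 50 per group each match a standard method, but not the same one. A two-sided test would need 63 (normal) or 64 (t) per arm and matches neither.

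**Power with 100 enrolled and some lost.** The same formula with fewer evaluable participants (n is the average per arm):

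| Assumed loss | Evaluable | n per arm | Power, t-test | Power, normal | d detectable at power .8 (t-test) |
|---|---|---|---|---|---|
| 0% | 100 | 50 | .799 | .804 | 0.50 |
| 5% | 95 | 47.5 | .781 | .786 | 0.51 |
| 10% | 90 | 45 | .761 | .766 | 0.53 |
| 20% | 80 | 40 | .716 | .723 | 0.56 |

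Against .799 with no loss, the cost is .799 − .781 = .018 at 5%, .799 − .761 = .038 at 10% and .799 − .716 = .083 at 20%. With one participant lost, power is .795 (t-test) or .800 (normal approximation).

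**Sensitivity to what 0.5 means.** Section 1.2 tests change. If 0.5 is instead the group difference at the post-intervention session, in units of the single-session SD, with no baseline difference and equal SDs, the effect on change is 0.5/√(2(1 − r)), where r is the pre–post correlation. The SAP gives no r, so these values are assumptions:

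| r | d on change | Power, 100 evaluable | 90 | 80 |
|---|---|---|---|---|
| .3 | 0.42 | .675 | .635 | .590 |
| .5 | 0.50 | .799 | .761 | .716 |
| .7 | 0.65 | .941 | .918 | .888 |

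The main figures coincide with r = .5. Over this range, r moves power more than a 10–20% loss does.

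**The case against.** The strongest reply is that only the SAP is at hand. Expected attrition, retention and replacement of withdrawals commonly sit in a protocol, and nothing in the SAP says that nobody will withdraw or that losses will not be replaced. This stands in part: it would be wrong to claim that the trial as a whole makes no provision for loss. It does not dispose of the point, because the SAP does its own calculation, sets enrolment from it, and attaches the power to that enrolment. The wording in section 1.1 can be corrected whatever the protocol says.

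Second, every loss rate here is assumed, and small losses hardly matter. This stands. A reader might infer that any loss at all takes the trial below adequate power. That is too strong: one loss leaves .795 or .800, depending on the method, and 5% costs under two points. A reader might equally infer that the trial is materially underpowered. The documents do not support that either, since they give no withdrawal rate.

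Third, a two-sample t-test is not literally the planned ANOVA. With two groups and two sessions, the interaction test is equivalent to a t-test on change scores, so the calculation fits if 0.5 is the effect on change. If it is the post-session difference, power at 100 could be .94 (r = .7) or .675 (r = .3). This stands as a condition on the figures, and it is why the edit should define the 0.5.

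Finally, the plan has not miscalculated: its inputs return .80 at 100 to two decimals. That is correct. The gap between 102 and 100 costs only .806 − .799 = .007. The point is about which participants the figure describes.

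**Conclusion.** The point holds in a limited form. Section 1.1 sets enrolment at 100 against a stated need of 102 (or 50 per group) and leaves no margin for participants without a post-intervention session. The power of .8 is therefore a statement about participants with both sessions. If 0.5 is the standardized group difference in change, with one-tailed alpha .05 and equal loss per arm, an assumed loss of 10–20% lowers power by about 4 to 8 points; a few losses are trivial. The SAP does not show how much loss to expect, so this is a matter of stating the power accurately and not evidence that the design fails. It is worth correcting because the correction is cheap and affects how a null result would be read.

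**What to change.** Keep enrolment at 100 and revise section 1.1 in one edit:

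1. State that the calculation refers to evaluable participants, meaning those with both the pre- and the post-intervention session.
2. Restate power and detectable effect at the sponsor's expected loss. Suggested text, with the range to be replaced by the sponsor's own figure: *With 100 enrolled and 10–20% lost before the post-intervention test (90 to 80 evaluable), power for d = 0.5 is .76 to .72, and the effect detectable with power .8 is 0.53 to 0.56.*
3. Say that 0.5 is the standardized group difference in the tested contrast, the time-by-group change. If it was meant as the post-session difference, give the assumed pre–post correlation and recompute.
4. Reconcile 102, 50 per group and 100. The t-test gives 51 per arm (102) and the normal approximation gives 50 per arm (100). Name the method and use one set of figures.

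The cost is a few sentences and a slightly less favourable stated power. No participants are added and no analysis changes. If the sponsor preferred to hold the power instead, enrolment would be 102/(1 − loss): 102/0.9 = 113.3, so 114 at 10%, and 102/0.8 = 127.5, so 128 at 20%. The correction does not require this.

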1.2 Statistics for Primary Outcome Measures

Virtual Multiple Errands Test (VMET): We will evaluate intervention efficacy by comparing the performance of the VR-EFT group to that of the VR-BHT group on performance-based measures of executive function ability related to daily life. This first test will evaluate near-transfer of intervention skills to the VMET, a test of executive functions evaluated in a computerized format. VMET requires working memory, planning, coordinating, and prioritizing, thus it serves as a global, performance-based measure of executive function. We will evaluate change on total number of errors from the pre-intervention baseline using a 2 (group) x 2 (testing session) repeated-measures ANOVA followed by Bonferroni-correct post-hoc tests to evaluate the significance of simple mean comparisons. We predict a significant time-by-group interaction in which the VR-EFT group will perform more accurately relative to the VR-BHT group at the post-intervention test, but not at the pre-intervention test. In the event that this measure proves insensitive, we will compute and analyze sub-scores based on strategy errors, completion errors, and rule-violation errors applying an additional Bonferroni multiple comparison correction for the use of three sub-measures.

TBI Awareness Questionnaire: We will evaluate far-transfer to overall Awareness score, which is a reflection of actions carried out in a real life setting. Performance (averaged over sub-domains) will be evaluated using a 2 (group) x 2 (testing session) repeated-measures ANOVA, followed by post-hoc tests corrected for multiple comparisons. We predict a time-by-group interaction with superior life outcomes reported by the Strategic Advantage group over the Informational Advantage group at the post-intervention time point only with no reliable differences expected at the pre-intervention phase.

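### The group-by-session ANOVA is an unadjusted change-score test: it gives up power against a baseline-adjusted analysis, and is biased if loss, or its relation to baseline, differs between arms

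*SAP*

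**What the plan says.** SAP section 1.2 sets the analysis of the Virtual Multiple Errands Test: "We will evaluate change on total number of errors from the pre-intervention baseline using a 2 (group) x 2 (testing session) repeated-measures ANOVA". The predicted result is a group-by-session interaction, followed by Bonferroni-corrected comparisons of simple means. For the second primary outcome, the Awareness score, it says: "Performance (averaged over sub-domains) will be evaluated using a 2 (group) x 2 (testing session) repeated-measures ANOVA". Section 1.3.1 carries the layout to the secondary measures: "These scores will be organized by primary domain and analyzed using 2 (group) x 2 (testing session) ANOVAs". That last sentence does not repeat the term repeated-measures, but the two factors are the same.

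Section 1.1 sizes the trial "for a one-tailed (Strategic Advantage > Informational Advantage) directional hypothesis", at an effect of 0.5 and power of .8, and ends: "Based on these analyses we plan to enroll 100 participants". The SAP mentions no baseline covariate, no model that keeps a participant with only one session, and no allowance for loss.

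**The concern.** With two sessions, the interaction F test is the square of the two-sample t test on change (post minus pre). Two things follow.

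- **Precision.** Subtracting the whole baseline score fixes its coefficient at 1. The coefficient that minimises variance is the pre-post correlation r (equal SDs), so the change score carries avoidable noise whenever r is below 1.
- **Bias under unequal loss.** A participant without a post score has no change score. If the remaining participants' baselines then differ between arms, regression to the mean moves their changes by different amounts, and an interaction can appear with no treatment effect.

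Both primary outcomes and every domain test share this method. Training runs over four weeks, so some loss is plausible, and the planned number leaves no margin for it.

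**Working it through.** **Inputs from the SAP (section 1.1).** Alpha .05 one-tailed, power .8, effect 0.5, two arms, 100 enrolled, taken as 50 per arm.

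**Assumed, because the SAP gives no value.** Pre-post correlation r; loss of 10% to 30%; the way loss depends on baseline; equal SDs at both sessions, set to 1; the 0.5 read as a multiple of the post-score SD.

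**1. The plan's own figure.** n per arm = 2 x (1.645 + 0.842)² / 0.5² = 49.5, so 50 per arm or 100 in total. The exact t calculation gives 51 per arm or 102. The stated 102 and the planned 100 are therefore both reproduced for a plain two-sample comparison with no loss.

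**2. Precision.**
- SD of change = √(2(1 − r)).
- Residual SD after baseline adjustment = √(1 − r²).
- Variance ratio, adjusted to change = (1 − r²) / (2(1 − r)) = (1 + r)/2, which is below 1 for every r below 1. At r = .5 it is 0.75.
- Power ≈ Φ(0.5 / (SD x √(2/n)) − 1.645).

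At r = .5 the SDs are 1 and 0.866.

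| Per arm | Change score | Baseline-adjusted |
|---|---|---|
| 50 (no loss) | Φ(2.500 − 1.645) = 0.804 | Φ(2.887 − 1.645) = 0.893 |
| 40 (20% loss) | Φ(2.236 − 1.645) = 0.723 | Φ(2.582 − 1.645) = 0.826 |

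The noncentral t distribution gives 0.80 against 0.89, and 0.72 against 0.82. By the normal formula with no loss, the pair is 0.68 against 0.84 at r = .3 and 0.94 against 0.97 at r = .7.

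**3. Bias with no true effect.** Let m be the mean baseline of those retained in an arm, measured from the mean of all randomised. Their expected post score is r x m, so their expected change is −(1 − r) x m. The interaction is therefore biased by (1 − r) times the between-arm difference in m, with the opposite sign.

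Take 20% loss in each arm, unrelated to baseline in one and, in the other, more likely with a worse baseline (logit slope 1.0 to 1.5 per SD):
- Slope 1.0: m shifts by 0.172 SD. The bias is 0.6 x 0.172 = 0.10 at r = .4 and 0.4 x 0.172 = 0.07 at r = .6.
- Slope 1.5: m shifts by 0.225 SD. The bias is 0.6 x 0.225 = 0.14 at r = .4 and 0.4 x 0.225 = 0.09 at r = .6.

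The range is 0.07 to 0.14 SD, or 14% to 28% of the planned 0.5. In simulation at 50 per arm, two-sided type I error was about .06 to .09. In the same one-arm pattern, the bias was 0.04 to 0.08 SD at 10% loss and 0.11 to 0.20 SD at 30%.

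**4. Other patterns of loss, about 20% overall, r from .3 to .7.**

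| Pattern | Bias of interaction (SD) | Two-sided type I error, r = .5 |
|---|---|---|
| Same relation and same rate in both arms | 0.00 | .049 |
| Same relation, 11% against 27% lost | 0.09 to 0.04 | .055 |
| Opposite relations in the two arms | 0.26 to 0.11 | .127 |

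Baseline adjustment gave a bias of 0.00 in every row and type I error of about .05.

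**5. Limit of the remedy.** When loss in one arm depended on the unseen post score, both analyses were biased: −0.15 SD with adjustment, −0.10 SD for the change score.

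**The case against.** A reader might infer that the SAP prescribes a completers-only primary analysis that is biased whenever loss relates to baseline. The document does not support that, for three reasons.

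- The SAP never says that leavers are deleted. Ordinary software does this, but a 2 x 2 ANOVA can be run on imputed data, and a rule for missing scores may stand in the protocol, which is not at hand. The loss-related part of the point is therefore conditional. The precision part is not, since it applies with complete data.
- Loss related to baseline in the same way and at the same rate in both arms gives no bias. Nothing in the SAP shows that loss will differ by arm.
- Leaving participants out is not enough to produce this bias. ANCOVA on only those with a post score also removes it. The fault is the missing baseline adjustment, and a mixed model on everyone randomised is one remedy among several.

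Two further objections carry some weight. The SAP predicts an arm difference after the intervention and none before it. In null simulations with 10% to 30% loss, an interaction together with a Bonferroni-significant post advantage for VR-EFT occurred in only 0.1% to 0.4% of trials, against 0.3% with no loss. However, the SAP does not make that joint pattern its rule for success, and the interaction test alone is inflated. Direction matters too. If worse participants leave VR-EFT, the bias works against the hypothesis, and one-sided error at 20% loss falls to about .02. If they leave VR-BHT, it rises to about .10 to .15.

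**Conclusion.** The point holds in two parts.

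**Precision.** The planned interaction test is less precise than a baseline-adjusted comparison at any pre-post correlation below 1. At r = .5, d = 0.5 of the post-score SD and 50 per arm, one-sided power is about 0.80 against 0.89 with no loss, and 0.72 against 0.82 at 20% loss. The planned test falls below the intended .8 once there is appreciable loss, whereas the adjusted one still meets it at 20%.

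**Bias.** As ordinarily run, the test is exposed to bias if the rate of loss, or its relation to baseline, differs between arms. The 0.07 to 0.14 SD belongs to one assumed case, so it shows what could happen and does not predict what will.

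It would also go too far to say that baseline adjustment makes the result safe under any loss. It protects only when missingness is random given baseline and arm. The change is worth making because it improves the analysis even if nobody is lost.

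**What to change.** In sections 1.2 and 1.3.1, replace the interaction test with a baseline-adjusted comparison of post scores, for both primary outcomes and the domain scores. Either form will do:

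- **Constrained longitudinal mixed model** on all randomised participants in their assigned arm: pre and post scores as outcomes, a baseline mean common to both arms, a post-by-arm term and unstructured covariance.
- **ANCOVA** of the post score on arm, with the baseline score as covariate.

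Name one as primary and report the post-session arm difference with a 95% CI. State the assumption that missingness is random given baseline and arm. Add one simple sensitivity analysis for loss that depends on the unseen post score, such as shifting the assumed post scores of leavers in one arm over a stated range. If the protocol already has a rule for missing scores, refer to it so that the two agree.

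The cost is a change of SAP wording and a little more analysis work. Both scores are already planned, so no new data are needed.

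### The 2x2 repeated-measures ANOVA is valid but generally less precise than adjusting for the baseline score already collected, and the pre-intervention group comparison says nothing about efficacy

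*SAP*

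**What the plan says.** Section 1.1 plans 100 participants and states "These individuals will be randomized into the two intervention arms". The inputs to its sample size are given as "For an alpha level of .05, and an anticipated effect of 0.5 (medium), and a power of .8", and the hypothesis is one-tailed in favour of Strategic Advantage. It does not say whether the effect of 0.5 is scaled on the post-intervention score or on change, and it gives no pre/post correlation.

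Section 1.2 sets the primary analyses. For VMET, the quantity of interest is change in total errors since baseline, and the method is described as "using a 2 (group) x 2 (testing session) repeated-measures ANOVA followed by Bonferroni-correct post-hoc tests". Efficacy is expected to show as an interaction between time and group, with the VR-EFT arm predicted to "perform more accurately relative to the VR-BHT group at the post-intervention test, but not at the pre-intervention test". The Awareness score gets the same 2x2 "repeated-measures ANOVA, followed by post-hoc tests corrected for multiple comparisons", again with no pre-intervention difference expected. The comparisons that make up the post-hoc family are not listed.

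In section 1.3.1 the neuropsychological domains are "analyzed using 2 (group) x 2 (testing session) ANOVAs", with no post-hoc tests mentioned. Nowhere is the pre-intervention score used as a covariate.

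**The concern.** In a randomized trial with one pre and one post measurement, the interaction test subtracts the whole baseline score from the post score, whatever the correlation between them. When that correlation is low to moderate, the subtraction adds noise. ANCOVA instead uses the slope that the data support. The trial has already collected the baseline score and may not be getting full value from it on either primary test. Section 1.1 sizes the trial to 80% power with no visible margin, so lost precision matters.

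The second part concerns the pre-intervention group comparison. Randomization means that any difference there is due to chance, so neither a significant nor a non-significant result bears on whether the intervention works. If that comparison is counted in the Bonferroni family, it also makes the post-intervention comparison harder to pass.

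**Working it through.** **Inputs.** From section 1.1: alpha 0.05, one-tailed, power 0.8, effect 0.5, about 50 per arm. Assumed, because the SAP gives no values: r = 0.3 to 0.8, and equal pre and post SDs unless stated otherwise.

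**The plan's own figure.** A one-sided two-sample t-test with effect 0.5 and 80% power needs 50.15 per arm by the noncentral t, hence 51 per arm or 102 in total. The normal approximation gives 50 per arm. Power at exactly 50 per arm is 0.799. The stated sample size therefore reproduces.

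**Step 1: what the interaction tests.** With two sessions, the interaction F is the square of the t statistic for change scores. A numerical check on simulated data gave 4.9696 both ways.

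**Step 2: error variances per participant.**
- Change score: SDpre² + SDpost² − 2r·SDpre·SDpost
- ANCOVA: SDpost²(1 − r²)
- Difference: SDpre² − 2r·SDpre·SDpost + r²·SDpost² = (SDpre − r·SDpost)²

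The difference cannot be negative and is zero only when SDpre = r·SDpost.

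**Step 3: equal SDs.** The variance ratio, ANCOVA to change, is (1 − r²)/(2(1 − r)) = (1 + r)/2. The change-score test matches ANCOVA at 50 per arm with 50/((1 + r)/2) per arm. If 0.5 is a post-score difference, the standardized effects are 0.5/√(2(1 − r)) for change (98 df) and 0.5/√(1 − r²) for ANCOVA (97 df). Noncentral-t power at 50 per arm:

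| r | Variance ratio | Matching n per arm | One-sided power, change / ANCOVA | Two-sided power, change / ANCOVA |
|---|---|---|---|---|
| 0.3 | 0.65 | 77 | 0.675 / 0.831 | 0.553 / 0.737 |
| 0.5 | 0.75 | 67 | 0.799 / 0.889 | 0.697 / 0.815 |
| 0.7 | 0.85 | 59 | 0.941 / 0.966 | 0.892 / 0.934 |
| 0.8 | 0.90 | 56 | 0.989 / 0.994 | 0.975 / 0.985 |

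Example at r = 0.3: change 0.5/√1.4 = 0.423; ANCOVA 0.5/√0.91 = 0.524.

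**Step 4: if 0.5 is standardized on change.** The planned test has one-sided power 0.799 at any r. The ANCOVA effect is 0.5/√((1 + r)/2), giving power 0.924, 0.889, 0.853 and 0.834 at r = 0.3, 0.5, 0.7 and 0.8.

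**Step 5: unequal SDs.** With k = SDpre/SDpost, the ratio is (1 − r²)/(1 + k² − 2rk). At r = 0.5 it is 0.75/0.75 = 1.00 for k = 0.5, 0.75/0.79 = 0.95 for k = 0.7, 0.75/1.00 = 0.75 for k = 1.0, and 0.75/1.24 = 0.60 for k = 1.2.

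**Step 6: validity.** Simulation with 5,000 one-sided trials per setting at r = 0.3, 0.5 and 0.7 gave type I error of 0.046 to 0.054 for the interaction and 0.045 to 0.053 for ANCOVA. Simulated power was 0.682 / 0.830, 0.800 / 0.892 and 0.943 / 0.969, in line with the table.

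**Step 7: the post-hoc family.** Suppose the family is the pre and post group comparisons, so two tests (an assumption). With a post-score effect of 0.5, two-sided power for the post comparison is 0.590 at 0.05/2 = 0.025, against 0.697 at 0.05. The interaction test is unaffected.

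**The case against.** The strongest reply is that nothing here is wrong. The 2x2 interaction is prespecified, valid and widely used, and it tests change from baseline, which is what section 1.2 says it will evaluate. If 0.5 is scaled on change, the planned one-sided power is 0.80 whatever the correlation. With equal SDs, a shortfall against that target needs both post-score scaling and r below 0.5. The gain may also be negligible: at r = 0.7 with SDpre/SDpost of 0.6 to 0.8, the variance ratio is 0.98 to 1.00. ANCOVA pays about 1% in variance (a factor of 1 + 1/96) for chance baseline imbalance, which moves its two-sided power at r = 0.5 from 0.815 to 0.811.

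All of this is correct, and it limits the point to efficiency. It does not reverse it. Apart from that 1% and one degree of freedom, ANCOVA does not lose; it gains on either reading of the effect scale with equal SDs; and nothing in the SAP shows that the correlation or SD ratio falls where the gain vanishes.

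On the pre-intervention comparison, it is fair to say that the predicted pattern is a hypothesis and not a decision rule, that the SAP never claims a null pre-test result as proof of efficacy, and that the two-test family is assumed. The comparison is therefore superfluous, not a source of bias in the main test.

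Section 1.3.1 omits the words repeated-measures. The precision point carries over there on the natural reading that the same participants are tested at both sessions.

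**Conclusion.** The point holds as a worthwhile efficiency improvement, not as an error that invalidates the analysis. The direction is certain from the algebra; the size is not, because the SAP states no correlation, SDs or effect scale. With equal SDs, the planned test has the precision that ANCOVA would reach with 65% to 90% of the participants for r between 0.3 and 0.8. That is material at low to moderate correlation and small at high correlation. With unequal SDs the gain can disappear, as at SDpre/SDpost = 0.5 with r = 0.5, or grow, as at a ratio of 1.2. The pre-intervention group comparison carries no evidence of efficacy under randomization; its only possible effect is to dilute the post-intervention follow-up comparison. For the domains in section 1.3.1 only the precision point applies.

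**What to change.** In section 1.2, make the primary test for VMET total errors and for the overall Awareness score an ANCOVA of the post-intervention score on group and pre-intervention score, and report the adjusted group difference with its 95% CI. Remove the pre-intervention group comparison from the post-hoc tests. Use the same model for the neuropsychological and ANAM domains in section 1.3.1. If participants with only a baseline score are to be kept in the analysis, a constrained-baseline mixed model is an option; simple ANCOVA drops them.

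The cost is revised SAP wording and a different model call on the same data, with no new measurements or participants. The change should be fixed before the outcome data are analysed.
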